Non-Interventional Study Protocol

Study Protocol Title	Comparative Effectiveness and Safety of Direct Oral Anticoagulants in Patients with Nonvalvular Atrial Fibrillation in the UK	
Version Identifier	Number 1.0	
Date of Last Version	22 December 2021	
Study Type	Non-Interventional Retrospective Comparative Effectiveness Study	
Research Question and Objectives	
This study aims to evaluate the incidence of stroke and other outcomes in association with direct oral anticoagulants (DOACs) as compared to each other (i.e., direct comparisons) among patients with nonvalvular atrial fibrillation (AFib) in the UK. Individual DOACs of interest include apixaban, rivaroxaban, edoxaban, and dabigatran.
 
The primary objective is to
 
 Estimate the incidence rates and evaluate the association of stroke (ischemic or hemorrhagic) for patients with nonvalvular AFib who initiated apixaban compared to rivaroxaban 
The secondary objectives are to
 
 Compare the incidence rates of stroke (ischemic or hemorrhagic) for patients with nonvalvular AFib who initiated: 
 apixaban compared to edoxaban, dabigatran, and DOACs class rivaroxaban compared to edoxaban, dabigatran, and DOACs class edoxaban compared to DOACs class dabigatran compared to DOACs class Estimate the incidence rates and evaluate the association of all-cause mortality, myocardial infarction, transient ischemic attack, major bleeding events, and major adverse cardiovascular events (MACE) for patients with nonvalvular AFib who initiated individual DOACs compared to those who initiated other DOACs. 	
Country of Study	United Kingdom	
Study Review Board	[name], MPH Chief Science Officer Aetion, Inc.	[name] Programme Director - Data NICE
Study Implementation Team	[name], SRPharmS Senior Principal Scientist Aetion, Inc. [name], MS Senior Principal Product Scientist Aetion, Inc. [name] Scientific Partnerships Lead Aetion, Inc.	[name] Senior Advisor in Data and Analytics NICE [name] Scientific Advisor in Data and Analytics NICE [name], MBChB Senior Analyst NICE

Comparative Effectiveness and Safety of DOACs in Patients with AFib in the UK

	[name], BS Scientist Aetion, Inc.
--	---

1. Table of Contents

Table of Contents	2
List of Abbreviations	3
Amendments and Updates	5
Milestones	6
Rationale and Background	7
5.1. Aetion's Research Collaboration with NICE	7

Amendment or Update No.	Date	Section of Study Protocol	Amendment or Update	Reason

Comparative Effectiveness and Safety of DOACs in Patients with AFib in the UK

4. Milestones

Milestone	Planned Date
Start of Data Extraction	September 2021
End of Data Extraction	November 2021
Diagnostics for primary comparison	December 2021
Registration in the EU PAS Register	January 2022
Interim Report *	January 2022
Final Report of Study Results	February 2022

* The interim report will comprise descriptive and primary objective results for primary comparison.

Comparative Effectiveness and Safety of DOACs in Patients with AFib in the UK

5. Rationale and Background

Health Technology Assessment (HTA) agencies, like the National Institute for Health and Care Excellence (NICE), are turning toward coverage with evidence development and/or managed access programs to allow additional time for data on the effectiveness of products to mature or be collected. Real-world data (RWD) has emerged as a potential strategy to collect additional evidence on the effectiveness of products after launch. HTA bodies are in the process of adopting real-world evidence (RWE), evidence generated from RWD, into their decision-making processes and setting standards for its use.

As NICE develops best practices on real-world evidence (RWE) use, it is exploring RWD comparative effectiveness studies as a way to enhance its decision-making and address uncertainties in its assessments and guidelines.¹ As part of NICE's five-year strategic vision,¹ NICE is initiating RWE research projects to fill known evidence gaps, to inform when and how RWE can be used in its decision-making, and to determine when after drug launch sample size is sufficient for comparative effectiveness analysis and if the results are consistent over time. NICE is interested in a proof-of-concept RWE comparative effectiveness study to inform these best practices.

5.1. Aetion's Research Collaboration with NICE

Aetion entered a research collaboration agreement (RCA) with NICE in 2021 to evaluate how RWE studies can be used to fill evidence gaps and reduce uncertainties in NICE assessment and guideline development. Aetion is collaborating with NICE to identify research questions relevant to NICE's RWE standards workstreams. Using the comparative effectiveness study described below, Aetion and NICE are collaborating on identifying fit-for-purpose real-world data, developing the protocol, executing the study using the Aetion Evidence Platform® (2021), software for real-world data analysis (Aetion, Inc. <https://www.aetion.com>), and piloting the Structured Template and Reporting Tool for Real World Evidence (STaRT-RWE)² for transparent reporting of study implementation.

5.2. Selection of Atrial Fibrillation as Proof of Concept Study

The safety and efficacy of direct oral anticoagulants (DOACs) compared to vitamin K antagonists (VKAs) in patients with atrial fibrillation (AFib) have been established in randomized clinical trials.³ In Europe, the following DOACs are approved to prevent venous thromboembolism, deep vein thrombosis, pulmonary embolism, and stroke in adults with AFib: Apixaban (Eliquis®, first authorised in the EU and the UK May 2011); dabigatran (Pradaxa®, March 2008); rivaroxaban (Xarelto®, September 2008); and edoxaban (Lixiana®, June 2015).^{4,5}

Between March 2012 and September 2015, NICE separately assessed and recommended four DOACs: dabigatran, rivaroxaban, apixaban, and edoxaban. Each submitted clinical trial compared the investigational DOACs to warfarin; however, there were no head-to-head clinical trials comparing the DOACs to each other at the time of NICE's assessments. Therefore, a network meta-analysis was completed for indirect comparison of individual DOACs agents using warfarin as the common comparator. NICE interpreted the network meta-analysis findings with caution noting the results were not sufficiently robust to differentiate between the products' effectiveness. These uncertainties were reiterated in NICE's 2014 AFib management guidelines in 2014 and 2021 updates.^{6,7}

Comparative Effectiveness and Safety of DOACs in Patients with AFib in the UK

The lack of relevant direct comparisons driving uncertainty is common at the time of NICE assessment, and these uncertainties are not unique to AFib. The uncertainties in comparative effectiveness of AFib treatments impact downstream decisions by healthcare providers and patients as they try to identify the most effective, safe, and cost-effective treatment option for stroke prevention.

NICE has selected AFib for the proof-of-concept comparative effectiveness real-world effectiveness (RWE) study in part because there is a growing body of literature that has successfully validated the use of real-world data (RWD) in AFib,^{8,9} and the burden of disease and cost to the healthcare system associated with AFib in the UK.⁷ In addition, the DOACs for nonvalvular AFib included in this study were approved more than 5 years ago in the UK (edoxaban was approved in June 2015¹⁰), which allows us to explore how the value of RWE comparative effectiveness changes with length of follow-up. This can help inform optimal timing for reassessments.

This study will not only inform when and how NICE could use RWE to address uncertainties in the clinical evidence, but it could also inform NICE's AFib clinical guidelines.

5.3. DOACs Therapies for Atrial Fibrillation

Atrial fibrillation (AFib) is the most common type of cardiac conduction disorder accounting for up to 2.6% of healthcare costs in Europe, and about 9.5% of the European population is estimated to have AFib by 2060.¹¹ In the UK, AFib affects 1.4 million patients,¹² and between 0.9% to 1.6% of UK's National Health Service (NHS) spendings are attributable to AFib predominately from hospitalizations.¹³ The condition is associated with significant complications, including stroke. Nonvalvular AFib increases an individual's risk of stroke by about five times,¹⁴ and between 20% and 30% of stroke cases are attributed to AFib.¹¹

Anticoagulants, including VKAs and DOACs, are highly effective in the prevention and treatment of thromboembolic events associated with AFib. Nevertheless, VKAs like warfarin are narrow therapeutic index drugs requiring frequent coagulation monitoring, and have multiple drug and food interactions. Alternatively, DOACs inhibit coagulation via direct and specific binding to active sites of thrombin (e.g., dabigatran) or factor Xa (e.g., apixaban, rivaroxaban, and edoxaban) of the coagulation pathway. Compared to VKAs, DOACs have a wider therapeutic index, which permits use in fixed doses without coagulation monitoring, and relatively limited drug and food interactions. Data from direct comparisons of DOACs (e.g., apixaban vs. dabigatran) are not available, and relative safety and efficacy findings are based on indirect comparisons from network meta-analyses.^{15,16} Healthcare providers face challenges from uncertainties around DOACs treatment decisions for patients with AFib, particularly around which individual agent has the best benefit-risk profile within the class for mortality and cardiovascular risk reduction.

The current protocol details a study designed to evaluate the effectiveness and safety of the DOACs of interest (apixaban, rivaroxaban, edoxaban, and dabigatran) in direct comparisons, among adults with nonvalvular AFib at risk for stroke in the UK.

6. Research Objectives

This study evaluates the comparative effectiveness of apixaban versus rivaroxaban (primary objective) for reducing stroke among patients with nonvalvular AFib in the UK.

Comparative Effectiveness and Safety of DOACs in Patients with AFib in the UK

Secondary objectives included comparing the effectiveness of apixaban and rivaroxaban to the other DOACs (edoxaban, and dabigatran).

6.1. Hypothetical Target Trial

When planning and designing RWE studies, it is important to consider emulating a hypothetical target trial.¹⁷ We sought to emulate a four-arm randomized trial that randomizes patients to apixaban, rivaroxaban, edoxaban, or dabigatran. The objective of the hypothetical trial is to compare apixaban to rivaroxaban, as the primary comparison, in the reduction of stroke among patients with nonvalvular AFib in the UK (Figure 6.1). The hypothetical target trial diagram is based on four clinical trials that evaluated the efficacy of respective DOACs in comparison with warfarin in patients with AFib (ARISTOTLE trial studied apixaban;¹⁸ ROCKET AF studied rivaroxaban;¹⁹ ENGAGE AF-TIMI 48 trial studied edoxaban;²⁰ and RE-LY trial studied dabigatran).²¹ In addition, comparisons of individual DOACs to other DOACs as a pharmacological class will be included as secondary comparisons. The hypothetical target trial would be powered for the primary comparison of apixaban versus rivaroxaban, and the study designed to meet diagnostic criteria for the main analysis.

Within the UK, apixaban and rivaroxaban are the most frequently prescribed DOACs (Figure 6.2). Secondary comparisons will include comparing apixaban and rivaroxaban to the two other DOACs (edoxaban and dabigatran) (Table 6.1).

[figure not shown]

Figure 6.1 Hypothetical Target Trial Design

Comparative Effectiveness and Safety of DOACs in Patients with AFib in the UK

[figure not shown]

Figure 6.2 Utilization of DOACs in the UK (April 2016 - January 2021; Source: OpenPrescribing)

Table 6.1 Direct Comparisons of Study Exposures of Interest

	Rivaroxaban	Edoxaban	Dabigatran	DOACs Class
Apixaban	Primary	Secondary	Secondary	Secondary (rivaroxaban, edoxaban, dabigatran)
Rivaroxaban	-	Secondary	Secondary	Secondary (apixaban, edoxaban, dabigatran)
DOACs Class	-	Secondary (apixaban, rivaroxaban, dabigatran)	Secondary (apixaban, rivaroxaban, edoxaban)	-

6.2. Primary Objective

The primary objective is to estimate the incidence rates and analogous hazard ratio of stroke (ischemic or hemorrhagic) for patients with nonvalvular AFib who initiated apixaban compared to rivaroxaban (see Table 6.1).

Comparative Effectiveness and Safety of DOACs in Patients with AFib in the UK

6.3. Secondary Objectives

The secondary objectives are to:

- Estimate the incidence rates and analogous hazard ratios of stroke (ischemic or hemorrhagic) for patients with nonvalvular AFib who initiated:
 - apixaban compared to edoxaban, dabigatran, and DOACs class
 - rivaroxaban compared to edoxaban, dabigatran, and DOACs class
 - edoxaban compared to DOACs class
 - dabigatran compared to DOACs class
- Estimate the incidence rates and evaluate the analogous hazard ratio of all-cause mortality, myocardial infarction (MI), transient ischemic attack (TIA), major bleeding events, and major adverse cardiovascular events (MACE) for patients with nonvalvular AFib who initiated individual DOACs compared to those who initiated other DOACs (see Table 6.1).

7. Data Source

This study uses anonymized patient RWD from The Health Improvement Network (THIN®) Database (A Cegedim Proprietary Database). THIN® is an unobtrusive medical data collection scheme that collects anonymised patient data from its members. THIN® data is a primary care research database containing anonymised electronic health record data from around 850 UK general practices (GPs) using the VISION clinical system (since 1994), containing records around 20 million patients, of which 2.6 million are currently active. THIN® collates the computerized medical records of general practitioners (GPs) in the UK who act as the gatekeepers of healthcare and maintain patients' life-long electronic health records. As such they are responsible for primary healthcare and specialist referrals, and they also store information stemming from specialist referrals, and hospitalizations. GPs act as the first point of contact for any non-emergency health-related issues, which may then be managed within primary care and/or referred to secondary care as necessary. The THIN® database includes demographic, medical diagnosis, patient medical history, lifestyle factors, and written prescription information on individual patients. The Quality and Outcome Framework (QOF) rewards practices for the quality care they provide their patients, based on a number of indicators, including medical record data entry.

The THIN® database has been used for scientific publications in AF and stroke research²²⁻²⁵ and has been validated and widely used in pharmacoepidemiologic studies.²²

8. Research Methods

8.1. Study Design

This study is a non-interventional, retrospective cohort study utilising RWD from the UK to address the study objectives. Patients with nonvalvular AFib who initiated (i.e., new users of) DOACs during the observation period will comprise the study cohort. The exposure groups of interest will be patients initiating individual DOACs (apixaban, rivaroxaban, edoxaban, and dabigatran). All patients will be followed for the first occurrence of each of the study outcomes of interest.

Comparative Effectiveness and Safety of DOACs in Patients with AFib in the UK

8.2. Setting

This study will be conducted using an electronic anonymized patient RWD from The Health Improvement Network (THIN®) Database (A Cegedim Proprietary Database) that includes data collected in primary care settings in the UK.

8.2.1. Study Population

This study will be conducted using patient clinical data extracted from the THIN® database in the UK for adults with nonvalvular AFib at risk for stroke who initiated DOACs between July 1, 2014 and December 31, 2020. This period was selected to minimize potential effects on recommended treatment options due to changes in AFib management guidelines. The NICE AFib management guidelines, which recommend prescribing a DOACs (apixaban, rivaroxaban, edoxaban, or dabigatran) for stroke prevention were published in June 2014⁶ and were not updated until April 2021⁷, thus we believe treatment options to be stable during this period. Patients with AFib are identified by Read Medical Codes and ICD-10 diagnosis codes.

Patient selection criteria are described in the following sections and Figure 8.1.

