8.3.1.4. Secondary Comparisons

- *Secondary Comparison 1*: initiators of apixaban vs initiators of edoxaban (i.e., *Exposure Group 1 vs Exposure Group 3*)
- *Secondary Comparison 2*: initiators of apixaban vs initiators of dabigatran (i.e., *Exposure Group 1 vs Exposure Group 4*)
- *Secondary Comparison 3*: initiators of apixaban vs initiators of other DOACs class (i.e., *Exposure Group 1 vs Exposure Group 5*)
- *Secondary Comparison 4*: initiators of rivaroxaban vs initiators of edoxaban (i.e., *Exposure Group 2 vs Exposure Group 3*)
- *Secondary Comparison 5*: initiators of rivaroxaban vs initiators of dabigatran (i.e., *Exposure Group 2 vs Exposure Group 4*)
- *Secondary Comparison 6*: initiators of rivaroxaban vs initiators of other DOACs class (i.e., *Exposure Group 2 vs Exposure Group 6*)
-
- *Secondary Comparison 7*: Initiators of edoxaban vs initiators of other DOACs class (i.e., *Exposure Group 3 vs Exposure Group 7*)
- *Secondary Comparison 8*: initiators of dabigatran vs initiators of other DOACs class (i.e., *Exposure Group 4 vs Exposure Group 8*)

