Confirm adequate sample size	
Adequate sample size will be defined as the minimum sample size required to achieve 80% power to detect a HR of ≥ 0.80 for the primary outcome of stroke under the assumptions of 1:1 matching ratio of the primary comparators (apixaban vs. rivaroxaban); a false-positive rate $\alpha=0.05$; a 1-sided test; and a background stroke incidence rate of 47 events per 100,000 person-years in patients with AFib³¹
 
Note: If adequate sample size is not reached (i.e., minimum HR

Comparative Effectiveness and Safety of DOACs in Patients with AFib in the UK

	
that we can detect is <0.80), it will not solely prohibit us from moving on to interventional analysis. NICE would typically use treatment effect estimates to parameterise economic models and as long as the uncertainty in estimates is quantified, it can be accounted for in decision-making. In addition, a recent article³² deprioritized the importance of power calculations for observational studies, noting that observational analyses with imprecise effect estimates should be completed as small studies can be pooled to provide a more precise effect estimate. Therefore, this analysis is informative even if the sample size is insufficient to detect a HR ≥ 0.80 with 80% power.

Confirm positivity of variables	
Propensity score distributions will be visually inspected, and overlap in all areas of the propensity score distributions will be confirmed.
 
Other approaches, such as propensity score weighting, will be explored to achieve covariate balance in case propensity score matching is insufficient.

Confirm baseline confounder balance	
The distributions of all potential confounders will be confirmed to be balanced for each comparison of interest. Covariate balance will be defined as ASD ≤ 0.10.
 
Although covariates with balance prior to propensity score matching may be removed from the propensity score model, balance of these covariates will still be confirmed after matching. Covariates with small residual imbalance (defined as $0.10 \leq \text{ASD} \leq 0.15$) may be deemed balanced if the covariate does not predict the outcome among the referent group (defined as ASD < 0.10 when comparing the risk of the outcome in those with the covariate vs. those without it) Evaluation of imbalance in outcome prediction will only be conducted once at the end of the diagnostic phase if all other diagnostic criteria are met.

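### The July 2014 index start is justified by stable treatment options, but the protocol dates edoxaban to June 2015, so the three edoxaban comparisons admit early comparators who could not have received it

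*Protocol*

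**What the plan says.** Section 8.2.1 takes adults "who initiated DOACs between July 1, 2014 and December 31, 2020" and applies that window to all exposure groups. The reason given is that the June 2014 guideline, described as recommending all four DOACs including edoxaban, was not updated until April 2021, "thus we believe treatment options to be stable during this period".

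Section 5.2 gives other dates. Its list of authorisations has "edoxaban (Lixiana®, June 2015", and the same section later repeats June 2015 as edoxaban's UK approval. It adds: "Between March 2012 and September 2015, NICE separately assessed and recommended four DOACs".

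Section 8.3.1.4 defines three comparisons with edoxaban as one arm:
- Comparison 1: "initiators of apixaban vs initiators of edoxaban"
- Comparison 4: "initiators of rivaroxaban vs initiators of edoxaban"
- Comparison 7: "Initiators of edoxaban vs initiators of other DOACs class"

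None has its own index start, and Sections 8.2.1.1 and 8.2.1.2 contain no criterion tied to availability.

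The plan has partial safeguards. Section 9 puts cohort entry year in the propensity score and matches 1:1 within a caliper of 0.01. Table 9.1 requires that "overlap in all areas of the propensity score distributions will be confirmed" and that confounders be balanced for each comparison. Section 9 also reports crude results beside the adjusted ones.

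**The concern.** The stability statement is the only reason given for the window, and it conflicts with Section 5.2: one of the four options was not yet available when the window opened. Section 6.1 sets out to emulate a trial randomising among all four drugs. Nobody could have been randomised to edoxaban before June 2015, yet initiators of the other drugs from that period count as its comparators.

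What is at stake is calendar-time bias. Lack of access to edoxaban is not itself confounding. But if stroke risk, prescribing or outcome recording drifted over time, non-contemporaneous comparators carry that drift into the edoxaban contrasts. The protocol treats calendar time as a potential confounder by including entry year in the propensity score.

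**Working it through.** **Inputs.** Window 1 July 2014 to 31 December 2020 (Section 8.2.1). Edoxaban June 2015, no day given, so 1 and 30 June are the bounds; NICE assessments of the four drugs ending September 2015 (Section 5.2). The protocol states no figure of its own to reproduce here.

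**Share of the window before edoxaban.**
- Window length: 2,376 days, counting both ends.
- 1 July 2014 to 1 June 2015: 184 days in 2014 + 151 in 2015 = 335; 335 / 2,376 = 14.1%.
- 1 July 2014 to 30 June 2015: 184 + 180 = 364; 364 / 2,376 = 15.3%.
- For reference, to September 2015: 427 to 456 days, 18.0% to 19.2%.

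**What a year term can separate.** All 2014 entrants precede edoxaban, so a categorical year isolates them. Within 2015, 151 / 365 = 41% to 180 / 365 = 49% of the year precedes authorisation. Those entrants share a year value with the late-2015 entrants, so year alone cannot tell them apart.

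**How many could survive matching.** The protocol gives no patient counts, so this is an illustration on assumed inputs: 8,000 comparators entering evenly over the window, 1,500 edoxaban initiators entering from 1 June 2015, five weak covariates, 1:1 nearest-neighbour matching with caliper 0.01, and one simulated data set per row. About 14% of eligible comparators precede edoxaban.

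| Entry year in the propensity score | Assumed edoxaban uptake | Matched comparators who precede edoxaban | Matched comparators from 2014 |
|---|---|---|---|
| Categorical | even | 3.8% | 0% |
| Categorical | rising | 0.2% | 0% |
| Categorical | steeply rising | 0% | 0% |
| Linear | even | 9.4% | 5.0% |
| Linear | rising | 1.5% | 0.3% |
| Linear | steeply rising | 0% | 0% |

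Section 9 does not give the functional form of entry year. In the worst categorical row, 0.038 × 1,500 = 57 pre-edoxaban comparators were matched out of 0.14125 × 8,000 = 1,130 eligible, about 5%. In the worst linear row it was 0.094 × 1,499 = 141 out of 0.14325 × 8,000 = 1,146, about 12%.

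**Crude results.** Matching does not touch these. The full 14% to 15% of calendar time stays in the comparator arms.

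**The case against.** The strongest reply is that the planned analysis already handles most of this. If edoxaban is the smaller arm (an assumption; Section 6.1 says only that apixaban and rivaroxaban are prescribed most), 1:1 matching estimates roughly the effect in edoxaban initiators. That requires only that each of them could have received the comparator, which holds throughout. Entry year is a listed covariate, so gross imbalance would show before outcomes are viewed. No calendar trend in stroke within 2015 is demonstrated, and crude results are unadjusted by definition. All of this stands and limits the size of the problem. It does not rescue the rationale sentence, separate entrants within 2015, or fix the form of the year term.

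A reader might infer three stronger things that the document does not support:
- **No chance of edoxaban until September 2015.** Section 5.2 has it approved in June. September is the end of a range covering four assessments; linking it to edoxaban is an inference, and not yet assessed does not mean unavailable.
- **Positivity is violated by design and the overlap check must fail.** Table 9.1 does not say whether overlap is judged before or after matching, it concerns estimated scores, and it allows weighting if matching is insufficient.
- **Unequal maximum follow-up biases the comparison.** Early comparators can have 6.5 years against about 5.5 to 5.6 for the first edoxaban initiators. That is administrative censoring, which person-time rates and Cox models accommodate.

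**Conclusion.** The contradiction between Sections 8.2.1 and 5.2 is real. It leaves about 11 to 12 months of indexing, 14.1% to 15.3% of calendar time, in which Comparisons 1, 4 and 7 accept comparators who could not have received edoxaban. Contamination of the matched estimates is probably small: 0% to 3.8% of matched comparators with categorical year and 0% to 9.4% with a linear term, under the assumed sizes and uptake. The crude results are unprotected. No bias in a hazard ratio has been quantified, and the document gives no data from which to do so.

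The primary comparison is unaffected, since Section 5.2 has both drugs authorised well before 2014. The pooled groups 5, 6 and 8 change composition when edoxaban arrives, but an alternative drug was available throughout, so the same argument does not apply to them. This is a weakness that should be fixed in three of eight secondary comparisons.

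**What to change.** 1. For Comparisons 1, 4 and 7, start indexing in both arms at a stated date of edoxaban availability, June 2015 by Section 5.2. A September 2015 start can be an optional sensitivity analysis. It should not be the main rule, because it also drops June to August 2015 initiators in both arms who are valid.
2. In those propensity models, specify entry time as categorical year or finer, for example quarter.
3. Keep July 2014 for apixaban versus rivaroxaban.
4. Correct the stability sentence and its description of the June 2014 guideline so that they agree with Section 5.2.

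The cost is one date filter, one recoded covariate and a modest loss of early comparators, few of whom would be matched anyway (at most 5% to 12% in the illustration). No edoxaban initiator dated on or after availability is lost. Quarters use more terms: June 2015 to December 2020 touches 1 + 2 + 20 = 23 quarters, so 22 indicators, or 22 × 12 = 264 exposed patients under the Table 9.1 minimum if each indicator counts as a covariate. Categorical year (2015 to 2020) needs 5 × 12 = 60. If edoxaban numbers are thin, categorical year with the aligned start is enough.
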